The sample size has been based on the primary outcome variable of VFDs over 28 days. The Phase IIb study in 81 patients with D-CytoFab has been used as an estimate of the between patient standard deviation (SD) (11.380). Assuming this SD holds for the current study, then 100 patients per group will provide 90% power to detect an underlying true difference in means between a dose of AZD9773 and placebo of 4.2 VFDs using a 10% one-sided significance level. Given this is an exploratory Phase IIb study, a 10% one-sided significance level is considered appropriate as this implies a 1 in 10 chance of a false positive finding which is consistent with the aim in Phase II of identifying a promising therapy.

The following efficacy endpoints will be subjected to formal statistical analysis: VFDs over 28 days and at Day 15 (over 14 days), 7-day mortality, 28-day mortality, mortality at Day 90, organ failure-free days at Day 15 (over 14 days), shock-free days at Day 15 (over 14 days) and ICU-free days at Day 15 (over 14 days). All other data will only be summarised.

All efficacy data will be summarised and analysed using the per protocol (PP) population (including only patients without important detected protocol deviations affecting the efficacy endpoints; data will be considered according to the actual treatment first received). Additionally, an intention-to-treat (ITT) analysis of the endpoints listed above for formal analysis will also be undertaken using the ITT population (all randomised patients will be included and data will be considered according to the randomised treatment).

For each of the endpoints subject to statistical analysis the following statistical comparisons will be performed: AZD9773 dose arm 1 versus placebo, AZD9773 dose arm 2 versus placebo, and combined AZD9773 dose arms 1 and 2 versus placebo. Although there are three primary comparisons, this is an exploratory Phase II study and consequently no adjustment for multiple comparisons will be made. The nominal significance level used will be 10% one-sided. However, it is important to note that the study has only been sized based on VFDs over 28 days; this study is not powered to detect a statistically significant difference in 7-day mortality, 28-day mortality or mortality at Day 90. In this case the confidence intervals (CIs) will provide a guide to the possible range of the true treatment effect. This may also be the case for the other secondary endpoints.

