3. STUDY OBJECTIVES

3.1 Primary objective

The primary objective is to evaluate the effect of two different doses of AZD9773 versus placebo on VFDs over 28 days in patients with severe sepsis and/or septic shock, who are receiving appropriate standard of care.

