4.2 Rationale for study design, doses and control groups

In a Phase IIb study conducted with D-CytoFab employing a loading dose of 250 units/kg followed by 9 doses of 50 units/kg every 12 hours, there was a significant, prompt and sustained suppression of plasma TNF α during treatment such that TNF α was undetectable in nearly all plasma samples obtained during the entire 5 days of active treatment. Modest and transient rises of TNF α in the treated group occurred in only 2 patients. These 2 patients had the highest baseline TNF α levels of the group, suggesting that dosing was in the optimal region. This dosing regimen was found to significantly improve clinical outcomes for the D-CytoFab-treated group with no adverse safety findings.

In a recently completed Phase IIa study (D0620C00004) conducted with AZD9773, similar effects on plasma TNF α were seen. This particular study was not powered to detect efficacy, but did demonstrate that loading doses of up to 750 units/kg and maintenance doses of up to 250 units/kg every 12 hours were well tolerated in patients with severe sepsis.

In this Phase IIb study, which is powered to detect an effect on the parameter of VFD as a measure of efficacy, both the 250/50 units/kg regimen and the 500/100 units/kg regimen will be evaluated to determine which dose regimen should be employed in further clinical studies to evaluate an effect of AZD9773 on 28-day mortality. Both of these dose regimens were well tolerated in the Phase IIa (D0620C00004) study and the 250 units/kg dose was also well tolerated in the earlier D-CytoFab study. A dose regimen lower than 250/50 units/kg was not included in this Phase IIb study because 250/50 units/kg produced significant clinical benefit with D-CytoFab and there is currently no tolerability concern with the doses chosen for this study. The higher dose will explore the possibility of increased benefit with more TNF α suppression and help define the therapeutic dose-response.

The optimal duration of therapy with an anti-TNF α agent is a balance between intervening to suppress TNF α bursts while not inhibiting the host inflammatory response for too long. A treatment period of 5 days was chosen for the Phase IIb study of D-CytoFab and for the recently completed Phase IIa study (D0620C00004) conducted with AZD9773. In this Phase IIb study the maximum treatment period will also be 5 days.

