13. STATISTICAL METHODS AND SAMPLE SIZE DETERMINATION BY ASTRAZENECA

13.1 General principles

A comprehensive SAP will be finalised before the last patient visit. All statistical analyses will be performed by PAREXEL. Any deviations from those analyses presented here and/or in the SAP will be detailed in the clinical study report. All outputs will be produced using SAS[®] version 9 or later in accordance with AstraZeneca standards.

All study data will be analysed after the 28-day follow up is complete for all patients. A further analysis will be performed using the Day 90 assessment to understand longer-term patient outcomes (survival and HRQoL).

The following efficacy endpoints will be subject to formal statistical analysis: VFDs, 7-day mortality, 28-day mortality, mortality at Day 90, organ failure-free days, shock-free days and ICU-free days. All other data will only be summarised.

All efficacy data will be summarised and analysed using the per protocol (PP) population. Additionally, an ITT analysis of the endpoints listed above for formal analysis will also be undertaken using the ITT population.

For each of the endpoints subject to statistical analysis the following statistical comparisons will be performed: AZD9773 dose 1 versus placebo, AZD9773 dose 2 versus placebo, and combined AZD9773 dose arms 1 and 2 versus placebo. Although there are three primary comparisons, this is an exploratory Phase IIb study and consequently no adjustment for multiple comparisons will be made.

Unless stated below, no imputation of missing data will be performed. All data recorded on the database will be included in data listings. Any spurious or erroneous data will be queried and followed up until satisfactorily resolved.

The nominal significance level used for this study will be 10% one-sided. However, it is important to note that the study has only been sized based on VFDs over 28 days; this study is not powered to detect a statistically significant difference in 7-day mortality, 28-day mortality or mortality at Day 90. In this case the confidence intervals (CIs) will provide a guide to the possible range of the true treatment effect. This may also be the case for the other secondary endpoints.

Demography data will be summarised using the PP and ITT populations and safety data will be summarised using the safety population. For all summaries of change from baseline, baseline is defined as the latest non-missing assessment prior to first study drug infusion.

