13.3.4 Ventilator-free days

Summary statistics (mean, median, standard deviation [SD], minimum, and maximum) of VFDs over 28 days will be presented by treatment group. Missing data will be handled using a last observation carried forward (LOCF) approach when calculating VFDs for each patient. A histogram of VFD will also be produced for each treatment group.

For the formal statistical analysis, an analysis of covariance model will be fitted for VFDs allowing for treatment group and the following baseline covariates:

APACHE II score (four categories based on the quartiles of the baseline score), age (two categories: <60 and 60 or older), region (three categories: Australia, North America [Canada & USA] and All Other) and an indicator variable if the patient was on mechanical ventilation at baseline (two categories: yes or no).

The difference in VFDs for each of the comparisons: AZD9773 dose 1 versus placebo, AZD9773 dose 2 versus placebo, AZD9773 dose 1 and 2 versus placebo will be presented in terms of the difference in the Least Square Means (LSMeans) and the associated two-sided 80% CI and one-sided p-value. Additionally, a two-sided 95% CI and two-sided p-value will also be presented.

For the PP population, the effect of other baseline variables (examples include baseline TNF, Xigris use prior to study treatment and presence of shock at baseline) on the treatment comparisons will also be explored via a series of analyses including the covariates as specified above for each of the levels of these baseline variables separately. The difference in the treatment LSMean and the associated two-sided 80% CI from these analyses (along with the results from the baseline covariates fitted in the statistical analysis above) will be presented graphically on the same plot. Additionally, an analysis of variance will also be performed for the PP and ITT populations (with no covariates and only treatment as a factor).

VFDs at Day 15 (over 14 days) will be analysed in a similar manner to above.

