13.3.6 Organ failure-free days, shock-free days, and ICU-free days

Organ failure-free days, shock-free days, and ICU-free days will be summarised and analysed in the same way as for VFD (see Section 13.3.4).

13.3.7 7-day mortality, 28-day mortality and mortality at Day 90

Seven-day mortality and 28-day mortality will be summarised by treatment group. The formal analysis will be undertaken for each the comparisons: AZD9773 dose 1 versus placebo, AZD9773 dose 2 versus placebo, AZD9773 dose 1 and 2 versus placebo separately using a Cochran-Mantel-Haenszel test in which the test will be stratified using the same covariates as for VFD. The corresponding relative risk, two-sided 80% CI and one-sided p-value will be calculated using the procedure PROC FREQ in SAS. Additionally, a two-sided 95% CI and two-sided p-value will also be presented.

An unstratified analysis will also be performed for the PP and ITT populations. Additionally, for the PP population, the impact of other baseline variables (examples include baseline TNF, Xigris use prior to study treatment and presence of shock at baseline) on the treatment comparisons will be explored by undertaking a series of analyses for each of the levels of these baseline variables separately, and the relative risks along with the associated two-sided 80% CIs from these analyses will be presented graphically.

In the event that the 7-day mortality and 28-day mortality status is unknown for some patients, they will be excluded from the PP population. However, for the ITT population they will be included as though they had died. Further sensitivity analyses may be undertaken depending on the number of such patients.

A Kaplan-Meier curve of time to death will also be produced and both a stratified (using the same covariates as for the analysis of 7 and 28-day mortality) and unstratified log rank test will be undertaken. If the 7-day or 28-day mortality status is unknown for some patients, they will be censored at the last known date the patient was alive.

Mortality at Day 90 will be considered in the same way as 7-day and 28-day mortality.

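### Two active arms are included to choose between regimens, but no planned output gives the dose 2 minus dose 1 difference with a confidence interval

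*Protocol*

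**What the plan says.** Section 4.2 gives the reason for having two active arms: both are evaluated "to determine which dose regimen should be employed in further clinical studies". It adds: "The higher dose will explore the possibility of increased benefit with more TNF α suppression and help define the therapeutic dose-response". Both statements concern the difference between doses.

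The formal primary objective in Section 3.1 is worded against placebo: "evaluate the effect of two different doses of AZD9773 versus placebo on VFDs over 28 days".

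The comparisons are set out as a definite list. Section 13.1 has "AZD9773 dose 1 versus placebo, AZD9773 dose 2 versus placebo, and combined AZD9773 dose arms 1 and 2 versus placebo", and the synopsis lists the same three. For VFDs, Section 13.3.4 says "AZD9773 dose 1 versus placebo, AZD9773 dose 2 versus placebo, AZD9773 dose 1 and 2 versus placebo will be presented in terms of" LSMeans differences, with 80% and 95% confidence intervals. Section 13.3.6 sends organ failure-free, shock-free and ICU-free days to the same analysis. For mortality, Section 13.3.7 has "AZD9773 dose 1 versus placebo, AZD9773 dose 2 versus placebo, AZD9773 dose 1 and 2 versus placebo separately using a Cochran-Mantel-Haenszel test". The protocol contains no dose 2 versus dose 1 contrast, no trend test across doses and no dose-selection rule.

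**The concern.** A trial that runs two active regimens in order to choose between them should report how far apart they are and how well that distance is known. Here two of the three comparisons set one dose against placebo, and the third pools the doses, which cannot separate them.

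The risk lies in interpretation. The two dose-versus-placebo results share a placebo arm, and each has its own chance of crossing the significance threshold. One dose can cross while the other does not even when the doses are equally effective. Without the direct contrast and its interval, the report has nothing to show how weak such an apparent dose difference is.

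**Working it through.** **Inputs.** SD 11.380, 100 per arm, design difference 4.2 VFDs and 90% power (Section 13.4); 10% one-sided (Sections 13.1 and 13.4); 1:1:1 allocation (Section 4.1). The protocol gives no expected difference between doses.

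**1. The plan's own figure.**
- SE of a difference between two arms = 11.380 × √(2/100) = 1.609 VFDs.
- Power = Φ(4.2/1.609 − 1.2816) = Φ(2.610 − 1.2816) = Φ(1.328) = 0.908.
- The stated 90% is reproduced (97 per arm would suffice). It applies to one dose against placebo.

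**2. Precision of dose 2 minus dose 1.** The arms are equal in size, so the SE is again 1.609. With the pooled error on 300 − 3 = 297 degrees of freedom:
- two-sided 80%: 1.2844 × 1.609 = ±2.07 VFDs;
- two-sided 95%: 1.9680 × 1.609 = ±3.17 VFDs.

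These use the unadjusted SD; covariate adjustment could narrow them. As a test the contrast is weak. For an assumed dose difference of 2.1 VFDs (half the design effect), power at one-sided 10% is Φ(2.1/1.609 − 1.2816) = Φ(0.023) = 0.51.

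**3. How often equal doses look different against placebo.** Give both doses the same true effect δ. The two test statistics each have mean δ/1.609 and, sharing the placebo arm, correlation 0.5. The chance that exactly one exceeds 1.2816 is 2 × [P(one given dose significant) − P(both significant)].

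| δ (VFDs) | P(one given dose significant) | P(both) | P(exactly one) |
|---|---|---|---|
| 4.2 (protocol) | 0.908 | 0.845 | 0.13 |
| 3.0 (assumed) | 0.720 | 0.582 | 0.28 |
| 2.0 (assumed) | 0.485 | 0.318 | 0.33 |

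**4. What the planned outputs already contain.** Write d1, d2 for the dose-versus-placebo estimates and V1, V2, Vc for the variances of the two single-dose contrasts and the combined contrast. The point estimate is d2 − d1. Its variance does not follow from V1 and V2 alone, because of the shared placebo arm. If the combined contrast is the equal-weight average of the two doses from the same model, which the protocol does not state, then Var(d2 − d1) = 2(V1 + V2) − 4Vc. With V1 = V2 = 11.38² × 2/100 = 2.590 and Vc = 11.38² × (1/100 + 1/200) = 1.943, this gives 10.360 − 7.770 = 2.590, and the square root is 1.609 as in step 2. A reader could rebuild the interval under that assumption, but no planned output displays it.

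**The case against.** The strongest reply is that the information is largely there. Subtraction gives the dose difference. Its interval may be recoverable from the combined contrast, and Section 13.3.4 also plans means and SDs by arm and a treatment-only analysis of variance. For mortality, the counts by arm give an unadjusted relative risk between doses. This stands, so it would be wrong to say that the dose difference cannot be estimated. The gap is in planned reporting of its uncertainty. For mortality the gap is somewhat larger, because each comparison is run as a separate stratified test and none is between doses.

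A reader might infer that the sponsor would pick the regimen by comparing two p-values. The protocol does not say so. It states no selection rule and reports estimates with intervals. Secondary objective 8 in Section 3.2 and Sections 7.7.2 and 12.4 plan PK-PD work, and TNFα and safety are measured in every arm. The discordance rates describe a possible misreading, not a planned decision rule. On the other side, the concentration-efficacy work in Section 12.4.3 is graphical and goes further only where appropriate, and concentration, unlike dose, is not randomised.

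It is also fair that the dose question sits in the rationale while the objectives in Sections 3.1 and 3.2 are against placebo, and that the contrast has little power. Neither removes the point. Section 4.2 is the protocol's own reason for two active arms, and Section 13.1 already relies on confidence intervals where endpoints are not powered. An analysis plan could add the contrast, but the protocol sets its comparisons out as a definite list in several places, and this one is not among them.

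**Conclusion.** The point holds as a mismatch between stated purpose and planned reporting. Choosing between regimens is given as a reason for the design, and no planned output shows the dose 2 minus dose 1 difference with its interval. That interval would be about ±2.07 VFDs (80%) or ±3.17 (95%), assuming the SD of 11.38 holds, 100 patients per arm contribute and no gain comes from covariates. The 95% half-width is about three quarters of the 4.2-VFD design effect (3.17/4.2 = 0.75), so the contrast would inform the choice without settling it.

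If the placebo comparisons were read as a dose comparison, equally effective doses would look different in about 13% of trials at the protocol's effect, and in 28% or 33% at the assumed smaller effects of 3.0 or 2.0. The validity of the three planned placebo comparisons is not in question, and nothing here bears on which regimen is preferable.

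**What to change.** Add the dose 2 versus dose 1 comparison to Sections 13.1, 13.3.4, 13.3.6 and 13.3.7, and carry it into the synopsis list:

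- for VFDs and the other free-day endpoints, the LSMeans difference from the same analysis of covariance model;
- for mortality, a further Cochran-Mantel-Haenszel relative risk with the same stratification;
- for each, two-sided 80% and 95% confidence intervals, labelled as unpowered estimation to support dose selection.

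The cost is one extra contrast per covariance model and one extra stratified run per mortality endpoint. No patients or data are added, and the three planned comparisons and their significance level are unchanged. The change should be made before unblinding.

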5. PATIENT SELECTION CRITERIA

Patient population should be selected without bias.

Investigators must keep a record of patients who entered pre-study screening by meeting inclusion/exclusion criteria but were never enrolled, eg, a patient screening log. To enter the study, each patient must meet all of the inclusion criteria and none of the exclusion criteria for this study. Under no circumstances can there be exceptions to this rule.

Patients will be recruited from health care-related institutions or facilities.

Summary of inclusion criteria (complete details are listed in section 5.1)

1. Adults with a first episode of sepsis during this hospitalisation (including transfer from another hospital) (Inclusion criterion 1).
2. Objective evidence of infection that requires parenteral antibiotics (Inclusion criteria 2 and 5).
3. At least 2 of 4 SIRS criteria in the 24 hours before organ dysfunction (must include either fever OR elevated white blood cells [WBC]) (Inclusion criterion 3).
4. Cardiovascular or respiratory dysfunction (Inclusion criteria 4 and 5).

Overview of exclusion criteria (complete details are listed in section 5.2)

[figure not shown]
1. Moribund (not likely to survive 24 hours) or significant comorbidities making survival for 3 months unlikely (Exclusion criterion 5).
2. Immunocompromising comorbidities or concomitant medications.
 - Advanced human immunodeficiency virus (HIV) infection ($CD4 \leq 50/mm^3$) (Exclusion criterion 4).
 - Stage III or IV cancer (see Appendix J) (Exclusion criterion 7).
 - Haemopoietic or lymphoreticular malignancies not in remission (Exclusion criterion 9).
 - Receiving radiation therapy or chemotherapy (Exclusion criterion 10).
 - Stem cell, organ or bone marrow transplant in the past 6 months (Exclusion criterion 11).

- THIS IS A PRINTED COPY OF AN ELECTRONIC DOCUMENT. PLEASE CHECK ITS VALIDITY BEFORE USE.
- High dose steroids or other immunocompromising drugs (Exclusion criterion 12).
 - Absolute neutrophil count <500 per μL not due to sepsis (Exclusion criterion 13).
3. Concomitant diseases:
- Cirrhosis with portal hypertension or Childs-Pugh Class C (Exclusion criterion 14).
 - Burns over > 30% of body surface area (Exclusion criterion 15).
 - New York Heart Association functional Class IV due to heart failure or any disorder (Exclusion criterion 16).
 - Deep seated fungal infection or active tuberculosis (Exclusion criterion 21).
 - History of chronic hypercarbia, respiratory failure in past 6 months or use of home oxygen in the setting of severe chronic respiratory disease (Exclusion criterion 23).
 - Neuromuscular disorders that impact breathing/spontaneous ventilation (Exclusion criterion 24).
 - Quadriplegia (Exclusion criterion 25).
 - Cardiac arrest in the past 30 days (Exclusion criterion 26).
4. Medication and allergy disqualifications.
- Previously received ovine derived products (CroFabTM, DigiFabTM) (Exclusion criterion 18).
 - Sheep product allergy or allergy to latex, papain, chymopapain (Exclusion criterion 18).
 - Treatment with anti-TNF agents within the last 8 weeks (Exclusion criterion 19).
5. Pregnancy or plans to breast feed upon resolution of sepsis (Exclusion criterion 17).

5.1 Inclusion criteria

For inclusion in the study patients must fulfil the following criteria.

1. Patients undergoing a first episode of sepsis during this hospitalisation (including transfer from another hospital).
2. Objective clinical evidence of infection; at least 1 of the following (see also inclusion criterion 5). Including:
 - Perforated viscus.
 - WBC and/or pathogens in a normally sterile body fluid.
 - Radiographic evidence of pneumonia.
 - Signs of a local source of infection such as cellulitis.
 - A syndrome associated with a high risk of infection (eg, ascending cholangitis).
 - Positive culture from blood or from another normally sterile body fluid prior to study drug administration.
 - Evidence of an infecting organism such as pneumococcal antigen or Legionella antigen.
3. Patients must meet at least 2 of the following 4 SIRS criteria at least one of which must be the core temperature criterion or the WBC criterion (see also inclusion criterion 5); these criteria do not have to be met simultaneously; the actual values and the date and time that the criteria were met will be collected.
 - Hypothermia by core temperature $<36^{\circ}\text{C}$, or hyperthermia $>38^{\circ}\text{C}$ measured via any means.
 - Heart rate (HR) >90 beats per minute.
 - Respiratory rate (RR) >20 breaths/minute related to septic event or partial pressure of arterial carbon dioxide (PaCO₂) <32 mmHg related to septic event or requiring mechanical ventilation related to septic event.
 - Total WBC absolute count >12000 cells/mm³ or <4000 cells/mm³. In the presence of granulocyte-stimulating factor, for those patients whose WBC absolute count is >12000 cells/mm³, they must have a fever and at least one other criterion (RR or HR).
4. Patients must meet criteria for cardiovascular and/or respiratory dysfunction (see also inclusion criterion 5). Newly developed organ failures must be due to the acute

THIS IS A PRINTED COPY OF AN ELECTRONIC DOCUMENT. PLEASE CHECK ITS VALIDITY BEFORE USE.

septic process and not be explained by a chronic condition or by effects of concomitant therapy. Time of onset of the protocol qualifying organ dysfunction/failure will be recorded. For cardiovascular dysfunction, the time of organ dysfunction/failure is defined as the time of initiation of vasopressors. The time of pulmonary dysfunction/failure is defined as the time that the patient meets the appropriate $\text{PaO}_2/\text{FiO}_2$ (or $\text{SpO}_2/\text{FiO}_2$ ratio) ratio while on mechanical ventilation (for organ dysfunction/failure definitions, see [Table 2](#)). An arterial blood gas or recording of the patient's SpO_2 value within 2 hours of intubation will be required otherwise the 24 hour clock will begin at the time of intubation. Patients who have been on mechanical ventilation for more than 48 hours prior to the CCC call cannot use pulmonary dysfunction as the qualifying organ failure. These patients can be enrolled if they meet criteria for cardiovascular dysfunction.

Table 2 Organ dysfunction/failure definitions

System / organ	Definition
Cardiovascular System	
Hypotension, as defined as a systolic blood pressure <90 mmHg, or a mean arterial blood pressure ≤ 65 mmHg requiring vasopressors despite a) a volume infusion of 20 mL/kg crystalloid or colloid equivalent over 4-6 hours before randomisation or b) 30mL/kg crystalloid or colloid equivalent in the 24 hours prior to randomisation after consultation with the CCC.
 
NOTE 1: If hypotension and vasopressor requirement is in the setting of intubation, the patient must still be vasopressor-dependent 1 hour after intubation. Patients requiring vasopressors prior to intubation are eligible for the study.
 
NOTE 2: 10 mL/kg of colloids = 20 mL/kg crystalloids.

Pulmonary Dysfunction	
Pulmonary dysfunction is defined as the patient requiring mechanical ventilation related to the septic process and having a $\text{PaO}_2/\text{FiO}_2 \leq 300$ (or $\text{SpO}_2/\text{FiO}_2 < 357$). However, if lung is the primary site of infection then $\text{PaO}_2/\text{FiO}_2$ must be <200 (or $\text{SpO}_2/\text{FiO}_2 < 214$). Arterial blood gas measurements are preferred but if unobtainable, SpO_2 will be sufficient. SpO_2 should be obtained for all patients. If $\text{SpO}_2/\text{FiO}_2$ is being used, saturation must be $\leq 97\%$. Otherwise, SpO_2 should be measured at a different FiO_2 if clinically appropriate, or arterial blood gases should be obtained and $\text{PaO}_2/\text{FiO}_2$ used instead.
 
Patients who have been on mechanical ventilation for more than 48 hours prior to the CCC call cannot use pulmonary dysfunction as the qualifying organ failure. These patients can be enrolled if they meet criteria for cardiovascular dysfunction.

Abbreviations: CCC = Clinical Co-ordinating Centre; FiO_2 = fraction of inspired oxygen; PaO_2 = partial pressure of arterial oxygen.; SpO_2 = Oxygen saturation by pulse oximetry.

5. Sepsis (infection + SIRS criteria) must be present prior to cardiovascular and/or respiratory failure. SIRS criteria and cardiovascular and/or respiratory failure do not need to be present simultaneously but SIRS criteria must have been demonstrated at some time within the 24 hours preceding the initial cardiovascular and/or respiratory failure, even if SIRS criteria have been present for more than 24 hours. In the case where the patient first presents with cardiovascular and/or

respiratory dysfunction due to infectious process (eg, a new hospital admission), SIRS criteria must be met prior to study drug administration.

Study drug administration must occur within 24 hours after the onset of qualifying cardiovascular and/or respiratory failure.

In addition to the above criteria, for inclusion in the genetic and/or biomarker research undertaken in this study, patients must fulfil the following criterion:

1. Provision of informed consent for genetic and/or biomarker research (by the patient or his/her legally authorised representative).

If a patient declines to participate in the genetic and/or biomarker research, there will be no penalty or loss of benefit to the patient. The patient will not be excluded from other aspects of the study described in this Clinical Study Protocol, so long as they consent.

